## **Changes to the protocol**

### **Patients**

No changes.

### **History and Clinical Neurologic Examination**

Dynamometer results are not presented because they duplicate manual testing without added value.

### **Electrodiagnostic Examination (EDx)**

No changes.

### **Ultrasonography (US)**

The ulnar hand muscle CSA results are not presented because they duplicate clinical testing without added value.

### **Randomization and Masking**

No changes.

## **Treatment**

No changes.

## **Sample Size Calculation**

The sample size was calculated using the initial primary outcome measure because we do not know the minimal clinically important difference for UNEQ.

## **Primary and Secondary Outcome Measures**

The initial primary outcome measure was the percentage of patients with: (1) no UNE symptoms or (2) symptoms markedly improved – only minor symptoms persist at 12 months follow-up. However, due to the inclusion of only patients with moderate or severe UNE in the present trial, and follow-up of only 12 months, the trial outcomes were much worse than expected based on our previous study results. That study also included patients with mild UNE and had a much longer follow-up of 2-3 years. Only 8 patients (13%) in the CTE arms of the present trial reached the primary outcome. Patients also often reported inability to reliably compare their current hand symptoms with symptoms one year ago. Therefore, as the primary outcome, we reported a comparison of patients' responses to standard UNEQ at the baseline and at 12-month follow-up. This outcome measure was also recommended by the authors of a recent Cochrane review.

As explained, we deleted instrumental measurements of the FDI muscle CSA using US and ADM/FDI muscle strength using a dynamometer, due to duplication of clinical gradings without added value, and a large number of secondary outcomes.

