### **History and Clinical Neurologic Examination**

The first examiner will collect demographic and clinical data using a standard questionnaire for assessment of UNE severity (UNEQ). The UNEQ considers the patient's numbness and tingling of the last two fingers, elbow pain, and changes in these symptoms with elbow

position. It also evaluates hand weakness. Questionnaire items are graded as: 1 – absent, 2 – mild, 3 – moderate, 4 – severe, or 5 – very severe. The final UNEQ score is calculated as the mean of the nine items. Patients will also report whether UNE symptoms: 1 – improved, 2 – remained unchanged, or 3 – worsened. The first examiner will also perform a focused neurological examination and graded: (1) muscle wasting of the first dorsal interosseous (FDI) and abductor digiti minimi (ADM) muscles (0 – absent, 1 – mild, 2 – moderate or 3 – severe); (2) muscle strength of FDI, ADM, and four indicator forearm muscles using the modified MRC scale; and (3) light touch and pin-prick sensation on the tip of the 5th and 2nd finger, ulnar sides of the 4th finger, palm, and hand dorsum as well as the forearm (0 – normal, 1 – moderately reduced, 2 – severely reduced or 3 – absent). For statistical analyses, the modified MRC scale will be transformed as follows: MRC grade 0 = 0, 1 = 1, 2 = 2, 3 = 3, 4 = 4, 4 = 5, 4+ = 6, and 5 = 7. Clinical UNE severity was graded: (1) *Mild* UNE – reduced sensation in the ulnar-innervated areas; (2) *Moderate* UNE – + ulnar hand muscle weakness, and (3) *Severe* UNE – + at least moderate ulnar hand muscle atrophy.

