## **Randomization and Masking**

The study will have a parallel trial design with a 1:1 allocation ratio, and a trial CONSORT diagram will be drawn. CTE and RCC patients will be separately randomized by one of the authors (SP), throwing dice as follows: (1) even number – surgical release, and (2) odd number – conservative treatment. In patients with bilateral UNE, the more affected arm will be randomized. Patients randomized to the surgical arm will be referred to a plastic surgeon. All included CTE and RCC patients (also those randomized to surgical release) will be given illustrated instructions showing arm positions they should avoid to prevent further ulnar nerve damage due to external compression.

The examiners will be blinded to the patient's study arm and the findings of other parts of the patient evaluation. During follow-up, examiners performing EDx and US examinations will be able to see a post-operative scar, but will be unaware of the patient group (i.e., CTE vs. RCC). Patients will not be blinded to treatment.

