### **Primary and Secondary Outcome Measures**

At 12-month follow-up (after surgery or the start of conservative treatment), all patients will be evaluated using the same protocol as during the initial evaluation. The primary outcome measure of the study will be the change in UNEQ score from baseline at inclusion of patients into the study and at 12-month follow-up.

The secondary outcome measures will be changes in: (1) clinical UNE severity; (2) atrophy of the ADM and FDI muscles; (3) strength of the ADM and FDI muscles using the modified MRC scale; (4) light touch sensation on the tip of the 5th finger; (5) ulnar MNCVmin across the elbow; (6) the amplitude of the ulnar CMAP on stimulation at D4; (7) the amplitude of the ulnar SNAP; (8) ulnar nerve CSAmax in the elbow segment; (9) ulnar nerve CSAmin in the elbow segment.

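### The initial primary outcome was replaced partly on the trial's own 12-month result, at an undated point, and no between-arm comparison of it is assigned in the plan

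*Combined protocol and SAP*

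**What the plan says.** The main plan, under Primary and Secondary Outcome Measures, states: "The primary outcome measure of the study will be the change in UNEQ score from baseline". It then lists nine secondary outcomes, beginning "The secondary outcome measures will be changes in: (1) clinical UNE severity" and otherwise covering examination, nerve conduction and ultrasound measures. None is a responder percentage.

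Under Changes to the protocol, the section of the same name explains that the initial primary outcome was the percentage of patients with no symptoms, or with marked improvement and only minor residual symptoms, at 12 months. The reasons given for replacing it are:

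- results: "the trial outcomes were much worse than expected based on our previous study results", followed by "Only 8 patients (13%) in the CTE arms of the present trial reached the primary outcome";
- recall: "Patients also often reported inability to reliably compare their current hand symptoms with symptoms one year ago";
- as added support, a recommendation in a systematic review that the reference list dates to 2025. Recruitment began in January 2019.

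The changes entry on Sample Size Calculation says: "The sample size was calculated using the initial primary outcome measure". The main Sample Size Calculation section instead uses the proportion perceiving improvement in each CTE arm at 6 months.

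The patient-reported change item, under History and Clinical Neurologic Examination, has three grades: "Patients will also report whether UNE symptoms: 1 – improved, 2 – remained unchanged, or 3 – worsened".

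On allocation, Randomization and Masking says "CTE and RCC patients will be separately randomized by one of the authors" and blinds the examiners. Statistics includes a two-sample Z-test for two proportions but ties it to no named outcome.

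**The concern.** The stated reasoning runs from an observed 12-month result to a new primary outcome. Such a choice can be harmless or harmful to the error rate, depending on what the people choosing had seen. A pooled count carries almost no information about the treatment difference. Results by arm on both outcomes carry a great deal. Without a date or a statement of who knew what, a reader cannot tell whether the UNEQ test keeps its two-sided 5% level.

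Separately, the replaced outcome has dropped out of the list of comparisons. Followed as written, the plan never compares between arms the outcome that the changes section says determined the sample size.

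**Working it through.** **1. What the pooled figure implies.** The only figure given is 8 patients, 13%. Computing 8/N: 59 gives 13.56%, 60 gives 13.33%, 61 gives 13.11%, 62 gives 12.90%, 63 gives 12.70%, 64 gives 12.50%, 65 gives 12.31%. So 13% fits 60 to 64 CTE patients (64 only if 12.5% is rounded up). Arm sizes are not stated. With 1:1 allocation by dice they need not be equal, so 30 to 32 per arm is an assumption. The sample size itself cannot be reproduced, because no final N, arm proportions or standardised difference is given.

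**2. What the pooled figure leaves open.** Take 31 per arm (assumed). The pooled proportion is 8/62 = 0.129, and SE = √(0.129 × 0.871 × 2/31) = 0.0851. With z = (difference in proportions)/SE:

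| Split | Difference (points) | z | Z-test p | Fisher p |
|---|---|---|---|---|
| 8-0 | 25.8 | 3.03 | 0.002 | 0.005 |
| 7-1 | 19.4 | 2.27 | 0.023 | 0.053 |
| 6-2 | 12.9 | 1.52 | 0.13 | 0.26 |
| 5-3 | 6.5 | 0.76 | 0.45 | 0.71 |
| 4-4 | 0 | 0 | 1.0 | 1.0 |

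The same 8 responders are compatible with a clear difference or none. At 7-1 the Z-test and Fisher's test fall on opposite sides of 0.05, so the method matters at these counts.

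**3. Type I error if only the pooled count prompted the switch.** Null trials were simulated with 30, 31 or 32 per arm, 13% responders and latent correlation between the outcomes from 0 to 1.0 (40,000 trials per setting), switching when the pooled count was 8 or fewer. The Mann-Whitney type I error given a switch was 4.6% to 5.0%: no inflation.

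**4. Type I error if by-arm results on both outcomes guided the choice.** The error is 1 − P(|Z₁| < 1.96 and |Z₂| < 1.96) for a bivariate normal pair with correlation ρ.

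- ρ = 0: 1 − 0.95² = 9.75%.
- Upper limit on ρ: a 13% binary outcome can correlate with ranks at most √(3 × 0.13 × 0.87) = 0.58, or with a normal score at most 0.63. These give 8.8% and 8.6%.

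The range is therefore about 8.6% to 9.75%. A correlation of 0.9 would give 7.0%, but a 13% binary outcome cannot reach it. The simulations in step 3 gave 9.2% to 10.1% for either test being significant. They run slightly higher because the Z-test alone has an exact size of 5.5% at 13%.

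**5. Precision of the restored comparison.** For a 4-4 split, the Newcombe 95% half-width is √[(p − l)² + (u − p)²], with l and u the Wilson limits for 4/n. At 31 per arm, p = 0.129, l = 0.051 and u = 0.289, so the half-width is 17.7 points. At 30 and 32 per arm it is 18.2 and 17.3.

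**6. What was known by arm.** The documents fix two facts. An author carried out the allocation, and a by-arm calculation of perceived improvement at 6 months was planned for the first CTE patients. Neither shows that 12-month results by arm were seen. Together they mean that blindness to arm cannot be presumed.

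**7. How the initial outcome was recorded.** The three-grade item has no level for marked improvement, so it cannot by itself yield the initial outcome. The documents do not say how the 8 were classified.

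**The case against.** The strongest reply is that the switch is already disclosed: the changes section gives the former definition, the pooled result, the reasons and the replacement. A difference between a changes section and the current plan is not in itself an error. UNEQ is a fixed nine-item mean with no recorded change to its scoring, and the low response rate and poor recall are sensible grounds for preferring it. A results report not available here may give the responders by arm.

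Most of that stands, and it lowers the severity. It does not supply the date, the decision-makers or the state of knowledge by arm. The reasons given support adopting UNEQ; they do not support leaving the former outcome without a comparison.

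It can also be said that the plan has a suitable test, since Statistics provides a Z-test for proportions. That is correct. The gap is an outcome to which no analysis is assigned, not a missing method.

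A reader might infer that the outcome was changed because of an unfavourable difference between arms. The documents do not support this: the only result cited is pooled, and an author's knowledge of allocation is not evidence that outcomes were tabulated by arm.

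**Conclusion.** The point holds as a should-fix. The primary outcome was changed at an undated time, partly on the trial's own pooled 12-month result, and the replaced outcome has no assigned between-arm comparison.

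A reader might go further and conclude that the UNEQ p-value is inflated. That is not shown. The error is near 5% if only the pooled count was known, and about 8.6% to 9.75% only if by-arm results on both outcomes guided the choice.

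Nor is it settled that the initial outcome really sized the trial. The changes section says so, but the main sample-size section uses perceived improvement at 6 months, which differs in both definition and time point.

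The error range assumes approximately normal test statistics and a 13% response rate. The p-values and interval widths assume equal arms of 30 to 32, and the widths also assume a 4-4 split.

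**What to change.** 1. In the main Primary and Secondary Outcome Measures section, add the initial outcome as a named secondary, labelled as the original primary outcome replaced after 12-month results. Report CTE responders by randomised arm with the difference and a 95% CI by a small-count method (Newcombe or exact). Listing it as a second primary beside UNEQ would leave two primaries with no hierarchy.
2. In the same section, label UNEQ change as the primary outcome adopted after 12-month results were known.
3. In the changes section, state the date of the decision, who made it and who had seen arm-level data. Unless the decision is documented as blind to arm-level results, do not call the UNEQ p-value confirmatory. Keep the recall and review arguments as rationale.
4. Reconcile the main sample-size section with the two changes entries on which outcome and time point sized the trial, and state how the initial outcome was recorded.

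The cost is a few lines of text and one CTE table from responses already counted; no new data are needed. The downside is that the restored comparison will be imprecise (about ±17 to 18 points under the assumptions above) and rests partly on recall that patients often called unreliable. The UNEQ claim also weakens if blindness to arm-level results cannot be documented.

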## Statistics

The large majority of numerical variables were distributed non-normally, and therefore, non-parametric descriptive statistics (i.e., median (25th–75th percentile)) and a non-parametric comparison test (Mann-Whitney U) were used.

